### **Outcome Data Collection**

*Primary outcomes (hospitalizations and arrests).* Hospitalization data will be collected from three sources: the Georgia Department of Behavioral Health and Developmental Disabilities (DBHDD, the State's mental health agency), the CSU in Savannah, and the CSU in Brunswick. Because DBHDD operates all state psychiatric hospitals, they have complete admission and discharge data for the study timeframe. However, DBHDD only collected CSU data beginning in January 2017; as such, the two CSUs serving as referral sites will also provide admission and discharge data for the full study period.

Arrest data will be provided by the Georgia Crime Information Center (GCIC), within the Georgia Bureau of Investigation (the lead state law enforcement agency), in the form of the participants' record of arrests and prosecutions (RAP sheets). GCIC receives monthly arrest reports from >600 state and local law enforcement agencies; this information is stored in GCIC's crime database and is summarized in the RAP sheet. To test our arrest-related hypotheses, we will extract all arrests for the 12 months after enrollment. Arrest data will be available for all participants.

*Secondary outcomes (housing and recovery).* Data collection for the two secondary outcomes will be collected in-person, though retention is expected to be difficult based on the serious psychosocial impairment of the study sample and experience in the initial study. Two housing-related measures will be used. The *Housing Satisfaction Scale* (HSS) has 19 items covering choice, safety, privacy, and proximity. The *Housing Instability Index* (HII) is a sum of 10 items that ask participants about their housing situations over the past six months; the time frame was adapted to four months for this study to match the follow-up timepoints.

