### **Data Analyses**

Between-group comparisons will rely on intention-to-treat analyses. Analyses involving hospitalizations and arrests will be performed using both binomial and Poisson generalized linear models for binary outcomes and counts, respectively. Analyses of change in housing and recovery measures will be performed using linear mixed models on all available data at each timepoint. Time in months will be used as a continuous predictor (growth curves) with measures at baseline, 4-, 8-, and 12-months. For the primary outcome analysis (12-month endpoint) the model structure will include group (ODR vs. CM), time, and group-by-time interactions, with a random intercept for subject. For those measures that indicate significant 2-group differences, we will compare ODR against ICM specifically, to further define effects (post-hoc analyses). For count/duration of hospitalizations and number of arrests, we will do conditional tests (comparing only those with non-zero values) to reduce the effects of zero inflation and get meaningful effect sizes across groups.

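### Both primary outcomes are tested in several forms, with no confirmatory test, alpha, success rule or multiplicity control named

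*Combined protocol and SAP*

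**What the plan says.** All references are to the combined protocol and SAP.

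- Outcome Data Collection names two primary outcomes: "Primary outcomes (hospitalizations and arrests". It does not say whether a positive trial needs both or either.
- Data Analyses models these outcomes "using both binomial and Poisson generalized linear models for binary outcomes and counts, respectively", so each has an any/none test and a count test.
- The same section adds a further layer: "For count/duration of hospitalizations and number of arrests, we will do conditional tests (comparing only those with non-zero values"). Its stated purpose is "to reduce the effects of zero inflation and get meaningful effect sizes across groups". These tests are labelled neither confirmatory nor exploratory.
- One sentence mentions a primary analysis: "For the primary outcome analysis (12-month endpoint) the model structure will include group (ODR vs. CM), time, and group-by-time interactions". It follows directly on the growth-curve text for housing and recovery.
- A follow-on step depends on significance: "For those measures that indicate significant 2-group differences, we will compare ODR against ICM specifically". The plan labels this step post hoc.

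No alpha or sidedness is stated anywhere. The only step taken against multiple measures is the Recovery Summary Score, which concerns secondary outcomes.

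**The concern.** When one outcome is tested in several forms, the results can disagree. Arrests might show no difference in the proportion with any arrest but a significant difference in the count. The plan does not say which result would answer the arrest question, or whether a finding on arrests alone would count if hospitalizations showed nothing. That choice could be made after the results are seen.

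Two things are at stake. If ODR has no effect, the chance that some form of some primary outcome reaches significance is well above the nominal level. A chance finding would also open the ODR-versus-ICM comparison for that measure.

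**Working it through.** **Plan's own figure.** There is none to reproduce. The documents give no alpha, sample size, power, event rate or overall error rate.

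**Inputs from the documents**

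- Primary outcomes: 2 (Outcome Data Collection).
- Explicit unconditional tests: 2 outcomes × 2 forms (binary, count) = 4 (Data Analyses).
- Conditional tests: hospitalization count, hospitalization duration and arrest count = 3, for a total of 7.
- An unconditional duration test is not stated. If one were run, the total would be 8.

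**Assumptions**

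- Two-sided 0.05 per test.
- Each test holds its own level.
- Any significant form is reported as a primary finding.

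**Step 1: independent tests.** The chance of at least one false positive among k tests is 1 − 0.95^k.

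- k = 2: 1 − 0.95² = 9.75%
- k = 4: 1 − 0.95⁴ = 18.5%
- k = 7: 1 − 0.95⁷ = 30.2%
- k = 8: 1 − 0.95⁸ = 33.7%

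Forms of one outcome share data and will usually be positively correlated, so these are upper values for the cases considered here.

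**Step 2: correlated tests.** Test statistics were drawn as correlated normals, 400,000 draws per setting. The correlation between the two outcomes was 0.2, and the correlation within an outcome was varied.

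| Within-outcome correlation | 4 tests | 7 tests | 8 tests |
|---|---|---|---|
| 0.3 | 17.8% | 28.0% | 30.9% |
| 0.5 | 16.9% | 25.7% | 28.0% |
| 0.7 | 15.8% | 22.1% | 23.7% |
| 0.9 | 13.4% | 16.6% | 17.4% |

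Steps 1 and 2 together give about 13% to 18% for four tests, about 17% to 30% for seven, and up to 34% for eight.

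**Step 3: simulated null data.** Counts were negative binomial, with gamma lengths of stay. Assumed values were total N of 160 or 240, 12-month event proportions of 0.40 and 0.25 or 0.60 and 0.40 (hospitalization and arrest), and between-outcome correlation 0.2. There were 3,000 trials per setting. Each form was compared by a t test, which stayed close to 5%, in place of the planned models.

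- 4 tests: 14.7% to 17.5%
- 7 tests: 22.2% to 24.8%
- 8 tests: 23.5% to 26.0%

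These fall inside the ranges from Steps 1 and 2.

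**Step 4: the individual level.** In the same simulated data, a plain Poisson test of a single count rejected in about 9% to 45% of null trials, because the counts were overdispersed. Steps 1 to 3 exclude this extra error. It matters for the remedy, though. With 120 per arm and overdispersed counts of assumed mean 1.0 and 0.6, Holm on two plain Poisson rate ratios gave an overall error of about 11% to 30%. With robust variance it gave about 5% to 6%.

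**Step 5: after correction.** One valid test per outcome without adjustment still gives 9.75% under independence. At 0.025 each the figure is 1 − 0.975² = 4.94%. Holm has the same first threshold and also keeps the overall error at or below 5%. If both outcomes must be significant, each by one named test, 0.05 each does not inflate the error.

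**Step 6: power cost.** Power of 80% at two-sided 0.05 implies a standardized effect of 1.960 + 0.842 = 2.802. At two-sided 0.025 the critical value is 2.241, so power is Φ(2.802 − 2.241) = Φ(0.561) ≈ 71%.

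**The case against.** The strongest reply is that the plan is silent on these matters and does not set out a faulty procedure. Several parts of that reply stand.

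- **No stated success rule.** A reader might infer that the plan allows success to be declared on any significant form. The documents do not say so. The sentence on significant measures only opens comparisons that the plan itself labels post hoc. What remains is that nothing prevents such a claim.
- **Role of the conditional tests.** Their stated purpose, handling zero inflation and obtaining effect sizes, fits a supportive role. One could also read the analysis as two-part: binary for any event, conditional for amount. If the conditional tests are descriptive, the seven-test range falls away, but the four explicit tests remain.
- **Number of tests.** A reader might count eight by adding duration in all participants. Duration appears only in the conditional sentence, so the text supports seven.
- **Separate hypotheses.** Outcome Data Collection speaks of hypotheses specific to arrests, so each outcome might be meant as its own family. Even then, two forms of one outcome compete without a ranking. If success required both outcomes, each by one named test, there would be no inflation, but the plan does not say this.
- **The primary-analysis sentence.** It might be thought to settle the matter. It names a 12-month endpoint and a model structure but no outcome or form. It leaves open whether the group term or the interaction is the test.

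**Conclusion.** The concern holds in a conditional form. Two primary outcomes are tested in four explicit ways, with three conditional tests added, and no confirmatory form, alpha, success rule or multiplicity control is given.

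Under the three assumptions listed in the working, the chance of at least one false positive is about 13% to 18% for the four explicit tests and about 17% to 30% for all seven. It could reach 34% only if an unstated unconditional duration test were also run. The conclusion does not depend on the conditional tests, since the four explicit tests alone give roughly three times 5%.

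A reader might want to quote one narrower figure as a property of this trial. The documents do not support that: the alpha, the number of confirmatory tests, the correlations and the success rule are all unstated.

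**What to change.** Amend Data Analyses before any analysis by arm. Enrollment was expected to run for about three years from December 2014, and the document was revised in July 2024. If results are already known, disclose the choice as post hoc.

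1. Name one confirmatory test per primary outcome, on all randomized participants, with the model and coefficient stated. One example is the 12-month count as an ODR/CM rate ratio, using negative binomial, quasi-Poisson or robust variance so that the test holds its level under overdispersion. The documents do not rank counts above the binary form, and either would cure the ambiguity.
2. Test the two with Holm at two-sided 0.05. Alternatively, state that both outcomes are required, in which case 0.05 each suffices.
3. Report the remaining forms (here binary, duration and conditional) as supportive estimates with confidence intervals and no significance claim.
4. For the primary outcomes, open the post-hoc ODR-versus-ICM comparison only for an outcome that passes.

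The change needs no new data. Its cost under Holm is that the smaller p-value must be at or below 0.025 before anything is claimed. For an outcome that has to pass at that level, 80% power becomes about 71%. The loss is smaller when the other outcome passes first, because the second is then tested at 0.05.

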### Referral, Assessment, and Randomization

All procedures will be reviewed and approved by the university's and the State's Institutional Review Boards. Clinicians at the three sites will refer potentially eligible patients who will then be evaluated for their interest in taking part in the study and capacity to give informed consent. Trained research assessors will complete the initial/baseline assessment

within about a week before discharge. After eligibility screening, consent, and the assessment, the patient will be randomized at a 1:1 ratio to ODR or CM using a computer-generated algorithm. The study statistician will create the randomization list, by randomly alternating blocks of 2 or 4, and the resulting sequential treatment assignments will be sealed in opaque envelopes. After the patient is found to meet eligibility criteria, gives informed consent, and completes the baseline assessment, the research assessor will open the next envelope in the sequence and inform the ODR or CM provider of the treatment assignment.

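### Housing and recovery (secondary) growth curves use only a random intercept, so the group-by-time test exceeds its nominal 5% if participants change at different rates or correlation fades over time

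*Combined protocol and SAP*

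**What the plan says.** The Data Analyses section assigns linear mixed models, on all available data, to change in the housing and recovery measures. On time it says: "Time in months will be used as a continuous predictor (growth curves) with measures at baseline, 4-, 8-, and 12-months". On structure it says that "the model structure will include group (ODR vs. CM), time, and group-by-time interactions, with a random intercept for subject". It names no random slope, serial correlation, unstructured covariance, robust variance, covariance check or fallback. Measures that differ significantly between the two arms go on to a post-hoc comparison of ODR with intensive case management.

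The sentence on model structure opens "For the primary outcome analysis (12-month endpoint". Outcome Data Collection, however, lists "Primary outcomes (hospitalizations and arrests") and, separately, "Secondary outcomes (housing and recovery"). Hospitalizations and arrests have their own binomial and Poisson models. The same section warns about follow-up of the in-person measures, "though retention is expected to be difficult based on the serious psychosocial impairment of the study sample".

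**The concern.** A random intercept lets participants differ in level but not in rate of change. It implies the same variance at each visit and the same correlation between months 0 and 12 as between months 0 and 4. In people with serious mental illness followed for a year after discharge, neither is assured. If either fails, the model treats the four visits as more informative about the slope than they are. The standard error of the between-arm difference in slope is then too small and the test rejects too often.

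At stake are the between-arm p-values and intervals for the housing and recovery measures, and the post-hoc comparisons that a significant result triggers.

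**Working it through.** The documents give no standard deviation, correlation, sample size or dropout rate for these measures, so there is no figure of the plan's to reproduce. Visit times and model terms are taken from Data Analyses. Everything else is assumed: baseline SD 1, two-sided 5% level, the same covariance in both arms.

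**Formula (complete data).** Centre the months: x = (−6, −2, 2, 6), Σx² = 80. Let S be the true 4 × 4 covariance of one participant's scores, and s² its mean variance minus its mean covariance.
- Slope variance according to the model, per participant: s²/80.
- True slope variance, per participant: x'Sx/80².
- Ratio R = x'Sx/(80 s²); true error = 2[1 − Φ(1.96/√R)].

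The number of participants cancels from R, so a larger trial does not help.

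**Constant correlation** (intercept variance 0.51, residual 0.49): x'Sx = 80 × 0.49 = 39.2 and 80 s² = 39.2. R = 1.00, error 5.0%.

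**Random slopes.** Let τ = (12-month slope SD)/12. Then R = (0.49 + 80τ²)/(0.49 + (80/3)τ²). For SD 0.5, τ² = 0.001736, R = 0.6289/0.5363 = 1.17, 1.96/√1.17 = 1.81, error 7.0%.

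| 12-month slope SD | R | Error of slope test |
|---|---|---|
| 0.3 | 0.5400/0.5067 = 1.07 | 5.8% |
| 0.5 | 0.6289/0.5363 = 1.17 | 7.0% |
| 0.75 | 0.8025/0.5942 = 1.35 | 9.2% |
| 1.0 | 1.0456/0.6752 = 1.55 | 11.5% |

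A correlation between intercept and slope does not enter this ratio.

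**Fading correlation.** Take AR(1) with correlation ρ per 4-month step and a share w of independent noise. Then x'Sx = 80 + 2(1 − w)(20ρ − 24ρ² − 36ρ³) and s² = 1 − (1 − w)(3ρ + 2ρ² + ρ³)/6.
- ρ = 0.7, w = 0.3: x'Sx = 80 − 14.15 = 65.85; s² = 0.6007; R = 65.85/48.05 = 1.37; error 9.4%.
- ρ = 0.9, w = 0.5: x'Sx = 80 − 27.68 = 52.32; s² = 0.5793; R = 52.32/46.34 = 1.13; error 6.5%.

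These are the ends of the range for ρ of 0.3 to 0.9 and noise of 30 to 50%. Noise-free AR(1) gives 8.7 to 16.0%; that is an upper extreme.

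**Check by simulation.** Random-intercept REML fits, with 100 or 240 participants in total and either full follow-up or 70/60/50% retained at months 4/8/12, gave slope-test errors of 4.5 to 6.0% under constant correlation, 6.8 to 8.2% at slope SD 0.5 and 11.6 to 13.8% at SD 1.0 (2,000 runs each; intercept and residual variance 0.5 each). The excess did not shrink at 240.

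**Does a random slope cure it?** With complete data and an unrestricted random-effects covariance, REML sets the variance of a participant's estimated slope to the observed variance of the individual least-squares slopes. The group-by-time test is then in effect a two-sample t-test on those slopes, so R = 1 whatever the true S. Under dropout this was simulated: 100 per arm, dropout more likely after a worse score, 41 to 42% missing at month 12, 14 covariance patterns, 6,000 runs each. The random-slope model rejected in 4.4 to 5.0% of runs and an unstructured categorical-visit model in 4.6 to 4.9%. A robust-variance model with categorical visits gave 4.7 to 5.0%; a robust-variance growth curve was not itself simulated under dropout.

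**The case against.** The strongest reply is that the excess depends on facts the documents do not contain. Under constant correlation there is none, and at slope SD 0.3 it is under one percentage point. The largest figures need individual 12-month changes that vary as much as the whole baseline SD, or an AR(1) process without noise. A random-intercept growth model is conventional, and the outcomes are secondary. All of this stands, and it limits the priority of the point. It does not justify leaving the restriction unexamined when the remedy is cheap.

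A reader might infer more than the documents support:

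- **That the 12-month contrast is undefined.** A level difference fitted at month 12 is another quantity one could take from this model, and its error rate differs (5.5 to 6.6% under AR(1) with noise). But the plan speaks of analysing change, of growth curves and of group-by-time terms. In a linear model the between-arm difference in change to month 12 is exactly 12 times the interaction, so that is the natural reading. One clarifying sentence is enough.
- **That the growth curve must be replaced by a categorical-visit model.** This is a trade-off. With complete data, 12 times the slope recovers 0.9 of the true month-12 difference both for a step at month 4 and for an effect seen only at month 12, and all of it for a linear course. Under about 42% dropout the figures are 1.00 for the step and 0.79 to 0.80 for the month-12-only effect. The protocol also places the start of enrollment in December 2014, over about three years, while the document is dated 2022 and revised 2024. Follow-up may be over, so a new main model could be post hoc.
- **That the Housing Instability Index will show a step.** Baseline comes before assignment ("After eligibility screening, consent, and the assessment, the patient will be randomized at a 1:1 ratio") and for recall "the time frame was adapted to four months for this study to match the follow-up timepoints". The baseline window therefore lies before assignment and the month-4 window after it. A between-arm step also needs a prompt effect that then stays constant, and nothing in the documents says so.

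**Conclusion.** The point holds as a conditional weakness in the secondary analyses and merits consideration. If slopes vary between participants or correlation fades, the planned group-by-time test is anti-conservative: about 5.8 to 11.5% for 12-month slope SDs of 0.3 to 1.0, and 6.5 to 9.4% for AR(1) with 30 to 50% noise, against a nominal 5%. These figures rest on assumed variances and correlations, and on complete data for the formula. Nothing in the documents shows where this trial lies in that range, so it cannot be said that the test will be inflated, only that the plan has no protection if it would be.

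The opening words of the model sentence might suggest that the primary outcomes are affected. They are not: hospitalizations and arrests are analysed by separate generalized linear models. The label is an editorial slip to reconcile.

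**What to change.** 1. Keep the growth curve. Add a random slope for time, correlated with the random intercept, fitted by REML with Kenward-Roger degrees of freedom.
2. If that model does not converge, use the random-intercept model with robust (sandwich) standard errors.
3. State that the tested quantity is the between-arm difference in change to month 12, that is, 12 times the group-by-time coefficient.
4. Add, as a sensitivity analysis for non-linear courses, a model with categorical visit, group-by-visit terms and unstructured covariance.
5. Reconcile the primary label in Data Analyses with the secondary status given in Outcome Data Collection.

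The cost is SAP wording, two more covariance parameters and somewhat wider intervals where the extra variance is real. With complete data the widening is about √R: √1.07 = 1.03 at slope SD 0.3 and √1.55 = 1.24 at SD 1.0. If outcome data have already been examined, say so and report the random-intercept result alongside.

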**A Trial of “Opening Doors to Recovery” for Persons with Serious Mental Illnesses**

**ClinicalTrials.gov: Identifier NCT04612777**

**09/13/2022**

**Revised 07/24/2024**

## Methods

### Participants

Enrollment will begin in December 2014 and continue until the target sample size is achieved, which is expected to take approximately three years. Adults with serious mental illnesses (SMI) will be recruited from three inpatient facilities: a state psychiatric hospital in Savannah, Georgia; a crisis stabilization unit (CSU) in Savannah; and a CSU in Brunswick, Georgia.

Eligibility criteria will include: (1) 18–65 years of age; (2) English speaking; (3) diagnosis of a psychotic or mood disorder (confirmed with the *Structured Clinical Interview for DSM-5 Disorders* (SCID-5); (4) two separate inpatient admissions, each for  $\geq 2$  days, in the past 12 months; (5) absence of intellectual disability or dementia; (6) capacity to provide informed consent; (7) being discharged to reside within one of seven counties with case management (CM) services provided by the public mental health agency hosting the research; (8) not currently receiving assertive community treatment (ACT) or CM; and (9) eligible to receive CM; i.e., unable to complete daily living activities in at least two areas, despite caregiver or behavioral health staff support, and requires assistance in one or more areas of managing their illness.

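### The housing and recovery mixed model is valid but inefficient: it fits a free arm difference at month 0, although baseline is measured before randomization

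*Combined protocol and SAP*

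**What the plan says.** Under Data Analyses: "Analyses of change in housing and recovery measures will be performed using linear mixed models on all available data at each timepoint". On time: "Time in months will be used as a continuous predictor (growth curves) with measures at baseline, 4-, 8-, and 12-months". Baseline is therefore part of the outcome vector. On the terms: "the model structure will include group (ODR vs. CM), time, and group-by-time interactions, with a random intercept for subject". No baseline covariate and no constraint on the baseline means is mentioned.

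The sentence with the model terms opens by referring to the primary outcome analysis at the 12-month endpoint. The trial's primary outcomes, hospitalizations and arrests, are assigned to binomial and Poisson models. Growth curves over four visits fit only the housing and recovery measures, so I read the sentence as applying to those.

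Under Referral, Assessment, and Randomization: "After eligibility screening, consent, and the assessment, the patient will be randomized at a 1:1 ratio to ODR or CM". The envelope is opened only after the baseline assessment is complete.

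Under Outcome Data Collection, housing and recovery are the secondary outcomes, collected in person, and "retention is expected to be difficult based on the serious psychosocial impairment of the study sample".

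**The concern.** With continuous time starting at zero, the group main effect is the arm difference in the fitted lines at month 0. Randomization follows the baseline assessment, so the expected value of that difference is zero and any gap seen is chance. The planned model still spends information on estimating it.

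The consequence is a wider standard error for the treatment effect on housing and recovery. These are the outcomes for which the plan expects follow-up losses, and the Recovery Summary Score is itself introduced to conserve power. The baseline values are already collected and already in the model, so better use of them needs no new data.

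**Working it through.** **Inputs from the documents.** Visits at t = 0, 4, 8, 12 months; linear time; random intercept only (equal correlation rho between visits); 1:1 allocation. The plan gives no precision or power figure to reproduce. Sample size is not stated, but it cancels from every ratio below.

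**Assumed inputs.** rho (shown from 0.3 to 0.9) and retention.

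**Group-by-time slope, complete data.** Σt = 24, Σt² = 16 + 64 + 144 = 224, Σ(t − 6)² = 80. Up to a common factor:

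- Free group intercept: information = 80/(1 − rho).
- Common baseline mean: information = D/(1 − rho), with D = 224 − 576·rho/(1 + 3·rho).
- Share of information lost by the planned model = 1 − 80/D. Reduction in standard error from the constraint = 1 − √(80/D).

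At rho = 0.5: D = 224 − 288/2.5 = 108.8, and 80/108.8 = 0.735.

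| rho | D | Information lost | SE smaller by | Power, if 80% as planned |
|---|---|---|---|---|
| 0.3 | 133.05 | 39.9% | 22.5% | 95% |
| 0.5 | 108.80 | 26.5% | 14.3% | 90% |
| 0.7 | 93.94 | 14.8% | 7.7% | 86% |
| 0.8 | 88.47 | 9.6% | 4.9% | 84% |
| 0.9 | 83.89 | 4.6% | 2.3% | 82% |

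The power column is illustrative (two-sided 5%): Φ(2.80/√(80/D) − 1.96).

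**Slope with dropout.** Assume monotone dropout and sum over patterns with n visits: A = Σp[Σt² − (Σt)²·rho/(1 + (n − 1)rho)]/(1 − rho), B = Σp·Σt/(1 + (n − 1)rho), C = Σp·n/(1 + (n − 1)rho). The share lost is B²/(A·C). For retention of 80/70/60% at 4/8/12 months and rho = 0.5, the pattern weights are 0.2, 0.1, 0.1 and 0.6. Then A = 141.49, B = 6.627, C = 1.443, and the loss is 43.91/(141.49 × 1.443) = 21.5%.

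| Assumed retention | rho 0.3 | rho 0.5 | rho 0.7 |
|---|---|---|---|
| 80/70/60% | 33.5% | 21.5% | 11.7% |
| 65/55/50% | 29.5% | 18.4% | 9.7% |
| 50/45/40% | 25.5% | 15.4% | 7.9% |

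At rho 0.8 to 0.9 the slope loss in these scenarios runs from about 2% to 7%.

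**Fitted 12-month difference, complete data.** In the common-baseline linear model this is 12 times the slope, so both contrasts give the same test. In the free model they differ. Variances on a common scale:

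- Free: (1 + 3·rho)/4 + 36(1 − rho)/80.
- Common baseline: 144(1 − rho)/D.

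| rho | Free | Common | Information lost |
|---|---|---|---|
| 0.3 | 0.790 | 0.758 | 4.1% |
| 0.5 | 0.850 | 0.662 | 22.1% |
| 0.7 | 0.910 | 0.460 | 49.5% |

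The dependence on rho is the reverse of that for the slope. Under the three retention scenarios the 12-month loss is 1.4% to 1.8%, 10.5% to 14.3% and 29.5% to 38.0% at rho 0.3, 0.5 and 0.7.

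**Other covariance.** If true slopes vary between participants so that the 12-month variance is 12% larger, the complete-data slope loss at rho 0.7 to 0.3 is 12.1% to 36.4%; if 48% larger, 7.9% to 28.9%. If correlation instead decays with time, with adjacent-visit correlation of 0.7 to 0.3, the loss is larger: 33.4% to 55.5%.

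**The case against.** **The planned model is conventional and valid.** This stands. A reader might infer that the group term biases the treatment comparison or inflates type I error. Nothing in the documents supports that: under randomization it does neither, and the outcomes affected are secondary. The point concerns efficiency only.

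**The size is not a property of the plan.** This also stands. A reader might take 15% to 40% as what the plan loses. That range needs rho between 0.7 and 0.3, complete data although losses are expected, the slope as the tested quantity, and precision read as inverse variance.

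**The free intercept has some value.** A reader might infer that it buys nothing. In fact, with complete data, the planned slope test is purely within-subject and unaffected by any arm difference in level. Blocks of two or four, with the assessor opening the envelope, leave some room for predictable assignment, although the envelopes are sealed and opaque. Nor is the chance baseline gap subtracted in full: its weight in the 12-month change implied by the slope is 12 × 6/80 = 0.9. These points argue for keeping the free-intercept model as a sensitivity analysis, not for making it the main one.

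**The constraint does not fit every planned comparison.** This stands. ICM goes only to controls in Chatham County, and the plan does not say that the post-hoc ODR versus ICM comparison restricts ODR to that county. Without that restriction the comparison is not randomized, and equal baseline means cannot be assumed.

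**The change comes late.** Enrollment from December 2014 for about three years plus 12 months of follow-up ends around December 2018; the document is dated 2022 and revised in 2024. On that schedule the data already exist. This affects how the change is labelled, not whether the constrained model is more precise.

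**Conclusion.** The point holds as a recommendation on efficiency for the secondary outcomes. Under the stated linear random-intercept model, and with equal baseline means from valid randomization, the common-baseline version was more precise for both contrasts at every rho and retention pattern tabulated above.

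The direction is secure; the size is not. It depends on rho, retention, the covariance structure and the contrast tested, none of which except the random intercept is settled by the documents. At rho near 0.5 the two contrasts lose similar amounts: about a quarter of the information with complete data (26.5% and 22.1%), and about 10% to 22% under the assumed retention. At high rho the slope loses little and the 12-month difference loses much, so the unstated contrast matters in its own right.

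**What to change.** In Data Analyses, for the randomized ODR versus CM comparison of the housing and recovery measures:

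- Specify time and group-by-time with one common baseline mean for both arms (constrained longitudinal data analysis), without a group main effect.
- Name the tested contrast: the month-12 difference or the slope.
- Keep the model with a free group intercept as a sensitivity analysis.
- Leave the post-hoc ODR versus ICM comparison outside the constraint unless ODR is limited to Chatham County participants.

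The cost is one model term, a few lines of text and one additional model fit per measure; no new data are needed. The downside is that the constrained model relies on equal baseline means and leans more on linear time: its slope is a poorer summary if a real effect is not linear, although the test stays valid when there is no effect. If arm comparisons have already been run, the constrained model should be reported as an added analysis and dated as such.
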